- To evaluate the safety of FMT in MS patients
- To evaluate tolerability of FMT in MS patients

Trial Design:

The proposed randomized, open label, controlled [treatment as usual control group], crossover study will be conducted in 40 patients (n=20 per group) diagnosed with the relapsing forms of multiple sclerosis according to the McDonald 2010 Criteria¹.

Based on the diagnostic criteria patients will be further screened to confirm eligibility and if eligible then consented.

Patients will be randomized 1:1 into two groups. One group will receive FMT, done by rectal enema administered by a RN, at baseline, month 1, month 2, month 3, month 4, and month 5 (early intervention group). The other group will receive treatment as per standard of care (treatment as usual control group) in the beginning of the study. For the last 6 months they will also receive FMT at month 6, month 7, month 8, month 9, month 10, and month 11 (late intervention group).

Clinical visits for both groups will be performed at baseline, and months 1 to 12 inclusive. During these visits a physical exam with vital signs, including a standardized neurological assessment Expanded Disability Status Scale – EDSS) will be done.

Patient's stools will be collected before each FMT procedure in both groups to evaluate gut microbial composition.

Urine will be collected to evaluate gut permeability at baseline, 6 and 12 months for both groups.

Peripheral blood samples also will be collected to evaluate circulating cytokine levels (IL-1 β , IL-2, IL-4, IL-5, IL-6, IL-9, IL-10, IL-12p70, IL-13, IL- 15, IL-17A, IL-17E/IL-25, IL-17F, IL-21, IL-22, IL-23, IL-27, IL-28A, IL-31, IL-33, GM-CSF, IFN γ , MIP-3 α , TNF α and TNF β) at baseline, months 1 to 12 inclusive for both groups.

Peripheral blood samples will also be collected to evaluate blood DNA bacteria at baseline, and months 1 to 12 inclusive for both groups.

Brain MRI with gadolinium [3T MRI machine at Robarts Research Institute] will be performed at baseline, 6 and 12 months for both groups as a safety biomarker [to rule out paradoxical effects; i.e. significant increase in MS activity as defined by Cutter's rule: 5 or more newly enhancing white matter lesions in the brain compared to the previous scan].

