Finally, fecal microbial transplantation is used to treat patients with recurrent *Clostridium difficile* infection (CDI), an antibiotic-associated bacterial colitis that may be life-threatening^{43,44}. Antimicrobial therapy disrupts normal intestinal microflora and facilitates CDI; transplantation of healthy donor stool is believed to restore fecal microbial diversity in the recipient and prevent CDI recurrence^{43,44}. As evidence of gut dysbiosis in MS mounts, FMT from donors free of autoimmune disease may be a consideration to restore microbial balance in those patients. Borody et al. reported neurologic benefit in three MS patients who underwent FMT for constipation⁴⁵. The neurologic improvement was dramatic, including recovery of bowel and bladder function and regained ability to walk. Nevertheless, enthusiasm for these findings is tempered by the absence of controls, the diagnosis of ‘atypical’ MS in two patients, and the unclear biologic plausibility regarding how FMT would reverse established MS disease burden. On this ground, we propose that fecal microbial transplantation from healthy donors to MS patients could restore microbial gut balance and ultimately influence disease activity.

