The use of antibiotics to reduce the gut bacterial load is protective against EAE, with reduced pro-inflammatory cytokine production and enhanced CD4+ T-regulatory cell proliferation^{30,48}. Yokote⁵⁶ et al. studied the possible effects of altering gut flora by antibiotic treatment on EAE. First, mice treated with kamamicina, colistina and vancomycin (KCV) had a change in their gut flora compared to the control group proved by DNA microarray analysis after KCV. The experimental mice group was treated starting one week before immunization. After the EAE induction, the experimental group had less clinical manifestations, less mononuclear cells infiltrations on lumbar spinal cord and reduced demyelination compared to the control group. Moreover, they also studied the cells response *in vitro* with antigen stimulation. Interestingly, the proliferation response of the mononuclear cells were not affected in the experimental group but they produced less inflammatory cytokines (IL-6 and 17) and showed a reduced expression of ROR, an important transcription factor for Th17, together with enhanced production of IL-10.

In summary, animal models suggest that the gut microbiota can powerfully modulate immune-mediated demyelination. Moreover, that inflammatory cytokines can be influenced by microbiota changes in a measurable fashion.

2.5 Rationale for the use of FMT for the treatment of multiple sclerosis patients

Gastrointestinal disorders have more data published in the literature on this matter. A recent systematic review by Chapman et al. of FMT for CDI included 29 studies, 2 of them randomized control trials, 4 prospective and 23 retrospective. The authors concluded that FMT is a highly effective therapy for refractory or recurrent CDI with a success rate of 83-100% with an acceptable safety profile⁵⁷. Another systematic review and meta-analysis by Sun et al. of FMT for ulcerative colitis (UC) identified 2 RCTs, 1 open-label case-control study, and 8 non-control cohort studies about the efficacy and safety of FMT in UC patients. They concluded that FMT may be an efficacious and safe alternative therapy for UC, at least when the standard therapy has failed or is unacceptable⁵⁸.

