Patients will also undergo a contrast-enhanced brain MRI scan at Robarts Institute in London Ontario. Other baseline assessments (prior to the first dose of therapy) include an EDSS, pregnancy test (if applicable), and physical exam. Blood samples are also taken at this visit in order to establish a baseline for routine chemistry/hematology. After all this assessments FMT will be performed by a trained nurse via a rectal enema

Patients will return to the clinic for visit 4 weeks after the first FMT. Another stool sample to evaluate the microbial before the second FMT will be collected. Also peripheral blood samples for cytokines and blood bacterial DNA analysis. This same routine procedure will be

repeated at month 2, 3, 4 and 5 for the early intervention group and at month 6, 7, 8, 9, 10 and 11 for the late intervention group. Both groups will come to clinic at baseline and month 1 to 12 inclusive, even if they are not receiving FMT. During all visits, a stool sample, a cytokine sample and a blood DNA bacteria sample will be collected. It is worth mentioning that at 6 and 12 months another urine analysis will be done to evaluate gut permeability and MRI study at Robarts Institute, London, Ontario for safety assessment will be performed for both groups.

Another safety assessment in each visit after FMT is to review of any adverse events that may have occurred. All patients receiving at least 1 week of treatment will be eligible for analysis.

Table 1. Early Intervention Group Schedule

[figure not shown]
Study Months	Pre-Visit	Baseline	Month 1	Month 2	Month 3	Month 4	Month 5	Month 6	Month 7	Month 8	Month 9	Month 10	Month 11	Month 12
Visit Duration	1.5hours	1.5hours	1.5hours	1.5hours	1.5hours	1.5hours	1.5hours	45min	45min	45min	45min	45min	45min	45min
Informed Consent Form	X													
Fecal Transplantation		X	X	X	X	X	X							
Height		X												
Weight, Vital Signs		X	X	X	X	X	X	X	X	X	X	X	X	X
Stool Sample		X	X	X	X	X	X	X	X	X	X	X	X	X
Urine: Gut Permeability		X						X						X
Circulating Cytokine Levels and Blood DNA		X	X	X	X	X	X	X	X	X	X	X	X	X
MRI		X						X						X
Routine Hematology and Urinalysis		X	X	X	X	X	X	X	X	X	X	X	X	X
Physical Exam/ EDSS		X	X	X	X	X	X	X	X	X	X	X	X	X

Table 2. Late Intervention Group Schedule

Study Months	Pre-Visit	Baseline	Month 1	Month 2	Month 3	Month 4	Month 5	Month 6	Month 7	Month 8	Month 9	Month 10	Month 11	Month 12

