5.2.2 Patient Exclusion criteria

- Not meeting all of the above inclusion criteria
- Pregnancy or breastfeeding
- Current or recent [in the last 90 days] exposure to high dose corticosteroids
- Ongoing use of antibiotics
- Presence of a chronic intestinal disease e.g. Celiac, malabsorption, Colonic tumor
- Inability to provide informed written consent.
- Immunosuppression from transplantation, HIV, Cancer chemotherapy or ongoing use of any immunosuppressive agents.
- Concomitant inflammatory diseases
- Any contra-indications for MRI. Participants are to be screened by a CMRTO certified MRI Technologist in order to determine the MRI compatibility or exclusion of implantable/external devices according to the manufacturer’s safety guidelines. The devices include cerebral aneurysm clips, neuro-stimulator, mechanical heart valves, cardiac stents, IUDs, vena cava filters, shunts, embolization coils, cochlear implants, non-removable prosthesis/artificial limbs. Contraindications are pacemaker of defibrillator, shrapnel/metallic fragments, previous brain surgery, seizure, severe claustrophobia, weight or body index that will prevent a successful MRI study.

5.3 Recruitment of trial patients.

Successful recruitment will be 3-6 patients per month on average. The goal is a total recruitment of 20 patients/12 months given the high numbers of competing studies, missed patients, consent failure rates and the refusal of an FMT strategy. We expect to monitor success with recruitment throughout the study and make revisions to recruitment procedures and eligibility criteria as necessary.

5.3.1 Recruitment of Healthy Volunteers.

Advertising will be posted throughout campus and hospitals in London announcing this study and calling for self-reported healthy individuals 18 y/o and older to participate in this study as a “control group”. We will recruit up to 10 [ten] volunteers. Participation will entail a single visit to the clinic for proper written informed consent prior to obtaining 1 tube, 5 ml of blood via standard of care venipuncture in one arm administered by a qualified registered nurse or lab technician. The tube with blood will be labeled with a study ID and sent to [name] lab for analysis in a completely de-identified fashion. This “control group” will not have any further participation in this study.

5.4 Adherence to protocol.

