6.2.5 Stool collection

Fecal samples will be collected from patients at baseline, and months 1 to 12 inclusive prior to receiving their scheduled FMTs. To collect the stool samples the participants will collect a piece of visibly soiled toilet paper and place it into a DNA-free bag. The bag will be transported to the Lawson Health Research Institute at St. Joseph’s Hospital and stored at -80 °C until the time of DNA extraction when all samples are collected. DNA will be extracted using the MO BIO Powersoil 96-well soil isolation kits, as adapted for the Human Microbiome Project. After DNA extraction, the V4 region of the 16S rRNA gene will be amplified using validated bar-coded PCR primer sets. After amplification, the samples will be sent for Illumina MiSeq sequencing (London Regional Genomics Centre). The reads generated from sequencing will be demultiplexed, taxonomically assigned by BLAST, and analyzed using the program R. Microbiome analysis will follow the protocol as described in Bisanz et al.⁴ A principal component analysis will be conducted and ALDEx2 tests will be performed to determine what the main differences in bacterial composition are between samples. The microbial composition at baseline will be compared to the other time points to determine how long it takes for the recipient to revert to their original microbiota. The donor microbiota will also be compared to each time point to determine how similar the patient’s bacterial composition is to the donors after transplant.

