APPENDIX A

Donor Screening Criteria

Donor inclusion criteria:

A healthy donor who has a normal body mass index (BMI of 18.5 – 24.9) and who satisfies the following criteria will be selected for the study and screened for all known potential transmissible agents.

Donor exclusion criteria:

- Any underlying metabolic disease including; hypertension, hyperlipidemia, diabetes, insulin insensitivity, atherosclerosis
- A history of any gastrointestinal or liver disorders or cancers. Including but not limited to; gastroesophageal reflux, peptic ulcer disease, celiac disease, inflammatory bowel disease (Crohn's disease or ulcerative colitis), microscopic colitis, motility disorders (including gastroparesis and irritable bowel syndrome) and diverticular disease.
- Previous surgery to the intestine, liver or gallbladder (except remote appendectomy).
- History of any malignancy
- Use within 3 months of any antibiotics or probiotics.
- Hospitalization within 3 months.
- Recent travel to a developing country (within 3 months)
- New Sexual Partner (within 3 months).
- Street drug use
- Family history of diabetes, early onset coronary disease or gastrointestinal or liver disease, colon cancer, familial malignancy
- Psychiatric history (major affective disorder, psychotic illness, ongoing use of any psychiatric medications)
- Any positive laboratory results for a transmissible pathogen
- Alcohol intake with a cut off value of <10g/d in women and <20g/d in men.

Donor laboratory screening: Summary of Tests and Procedures for Donor Screening is given below. For information purposes only.

Visit	Tests and Procedures

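### Recipients need only be off antibiotics on the day they enter, so the comparisons against each patient's own baseline can mistake recovery after a recent course for an FMT effect

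*Combined protocol and SAP*

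**What the plan says.** The recipient exclusion in section 5.2.2, repeated in the synopsis, is "Ongoing use of antibiotics". It has no look-back, and neither list mentions probiotics. The same list does set a look-back for another exposure: "Current or recent [in the last 90 days] exposure to high dose corticosteroids". For donors, Appendix A excludes "Use within 3 months of any antibiotics or probiotics".

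The background sections say why antibiotics matter here. Section 2.3 states "Antimicrobial therapy disrupts normal intestinal microflora and facilitates CDI". Section 2.4, on animal work, states "The use of antibiotics to reduce the gut bacterial load is protective against EAE, with reduced pro-inflammatory cytokine production".

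Two planned comparisons are made against the patient's own baseline. Section 6.2.5 compares baseline stool with the later time points "to determine how long it takes for the recipient to revert to their original microbiota". Section 6.2.3 compares cytokines at baseline with those at 12 months to decide whether FMT had an effect. Section 7.0 also frames cytokine efficacy as change from baseline within patients.

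The design has a concurrent control as well. The synopsis says "Patients will be randomized 1:1 into two groups", and section 4 says "Both groups will come to clinic at baseline and month 1 to 12 inclusive, even if they are not receiving FMT". Section 9.3 plans a mixed-design ANOVA between the two groups. Sections 6.2.1 and 6.2.2 record concomitant medications at baseline and at later visits, but no analysis uses that record.

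**The concern.** A recent antibiotic course leaves the flora disturbed, by the protocol's own account. If the baseline stool is taken at that point, two things go wrong in the comparisons that use baseline as the reference.

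- The flora may recover without any treatment over the following months. In the early-intervention group this happens while FMT is being given, and a before–after comparison cannot tell the two apart.
- The baseline sample is not the patient's usual state, so time to reversion is measured against the wrong target.

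At stake are the microbiome change, how long the transplanted flora persists (a stated interest in section 11.4.2), and the baseline-to-12-month cytokine comparison. An antibiotic course during the study is a separate disturbance. It can make the transplanted flora seem to last less long, and nothing in the plan marks the samples it affects.

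**Working it through.** The plan gives no figure to reproduce, so the check has three parts.

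**1. Which patients are exposed.**
- Early group: FMT at baseline and months 1–5. Recovery after a pre-baseline course overlaps with FMT.
- Late group: first FMT at month 6, with stool taken before it. That gives 7 samples before any FMT (baseline and months 1–6), so recovery in the first months shows as change without treatment. A disturbed baseline still enters the section 6.2.3 comparison and the reversion reference for these patients.
- Samples after the last FMT: the early group has months 6–12, so 7 × 20 = 140. The late group has month 12 only, so 1 × 20 = 20. The early group thus supplies 140/160 = 87.5% of the scheduled persistence data.

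**2. How many patients.** The documents give no rate of antibiotic use. Assume 5–15% finished a course shortly before baseline: 20 × 0.05 = 1 and 20 × 0.15 = 3 early-group patients. The chance of at least one in that group is 1 − 0.95^20 = 64% at 5% and 1 − 0.85^20 = 96% at 15%.

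**3. What this does to each comparison.** Let p be the share of recent users and δ the recovery shift in an affected patient, in SDs of the within-patient change (assumed 1 or 2). The expected bias within a group is p × δ. Between randomised groups it is pδ − pδ = 0, with a chance bias of SD δ√(2p(1−p)/20). A simulation of 40,000 trials per scenario, with 20 per group, no true FMT effect and two-sided 5% t-tests, gave:

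| p | Within-group bias (SD), δ = 1 / 2 | Within-group false positives, δ = 1 / 2 | Between-group false positives, δ = 1 / 2 | SD of chance bias, δ = 1 / 2 | Groups differ by 3 or more users |
|---|---|---|---|---|---|
| 5% | 0.05 / 0.10 | 5.5% / 6.1% | 5.1% / 4.9% | 0.07 / 0.14 | 6.7% |
| 10% | 0.10 / 0.20 | 6.9% / 10.0% | 5.1% / 4.9% | 0.09 / 0.19 | 18.0% |
| 20% | 0.20 / 0.40 | 12.0% / 24.5% | 5.1% / 5.1% | 0.13 / 0.25 | 32.0% |
| 30% | 0.30 / 0.60 | 21.0% / 45.8% | 4.9% / 5.0% | 0.14 / 0.29 | 38.7% |

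The 15% case lies between the 10% and 20% rows. The between-group test keeps its error rate throughout. What remains there is added noise and, in a single trial of this size, chance imbalance.

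**The case against.** The strongest defence is the design. Recovery after a pre-baseline course occurs in both randomised groups, both are sampled monthly, and section 9.3 compares them. This stands: for months 0–6 the expected bias is zero. Section 6.2.5 also compares each time point with the donor, and that comparison does not use the patient's baseline as its reference. It is fair to add that the study is exploratory (section 9.1), that time to reversion is not a listed primary or secondary objective, and that at low rates of use the inflation of error is modest.

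Several stronger readings are tempting, and the documents do not support them.

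- *The donor and recipient rules contradict each other.* Section 5.1 presents donor screening as the supplying laboratory's own procedure, given as background. It qualifies the transplanted material and does not define a recipient baseline.
- *The protocol says antibiotics lower patients' inflammatory cytokines.* The statement in section 2.4 is about mice with EAE. Taken at face value, recovery would raise inflammatory cytokines and could hide a benefit, so the direction of any cytokine bias is open.
- *Probiotic users should be excluded too.* A patient on steady probiotics has no recovering flora, and the documents show no route from such use to this bias.
- *Flora recovers within 3 months.* The documents do not say so.

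The defence does not reach the comparisons in sections 6.2.5 and 6.2.3, which make no use of the control group. After month 6 there is no FMT-naive comparator at all, because the late group is then receiving FMT.

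**Conclusion.** The point holds for the baseline-referenced comparisons and mainly for the early-intervention group. At an assumed 5–15% recent use, about 1–3 of its 20 patients would have a disturbed reference for all 12 later samples. With δ of 1–2 SD, the within-group bias is 0.05 × 1 = 0.05 to 0.15 × 2 = 0.30 SD. The inflation of false positives is modest at 5–10% use and becomes material only nearer 20%. The firmer harm is the invalid reversion reference in each affected patient, in the group that supplies nearly all the persistence data.

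A reader might infer that the randomised comparison is biased or that the cytokine result as a whole is compromised. Neither follows: the month 0–6 between-group analysis is protected in expectation. Both the rate of use and the size of the shift are assumptions. The point is a cheap improvement to the plan and not a fatal flaw.

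**What to change.** 1. In section 5.2.2 and the synopsis, extend the antibiotic exclusion to a stated look-back before baseline. The 3 months in Appendix A is an available precedent, though not evidence of how long recovery takes. Screening must ask about completed courses, which a list of current medications can miss.
2. Record probiotic use as a concomitant medication, and do not exclude for it.
3. In the microbiome and cytokine analyses, flag every sample taken within the same window after an antibiotic course, using the medication record already kept, and report results with and without those samples. With monthly visits and a 3-month window, one course flags about 3 of a patient's 13 samples.
4. State that change is attributed to FMT from the randomised month 0–6 between-group comparison, and that the comparisons in sections 6.2.3 and 6.2.5 are descriptive support.

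Treatment of infections during the study stays with the physician. The cost is one eligibility sentence, one sensitivity analysis and a wait for a few patients. That wait is a real but small burden, given the target of 20 patients in 12 months in section 5.3.

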5.5 Safety

We will monitor patients closely for potential adverse events. We plan to administer the FMT through a standard rectal enema done by a trained Registered Nurse. Full screening of the donor to rule out transmissible blood-borne, or fecal pathogens, as well as history and physical examination to rule out any underlying health conditions [as performed in previous studies^{70,71} and as recommended in the recent Guidance document from Health Canada], will assure the safety of the procedure. It is important to note that FMT has been found to be extremely safe in multiple previous studies, with no documented complications ever reported when performed in medically stable patients.

6. TREATMENT OF PATIENTS

6.1 Study Drug

Fecal microbiota.

6.2 Study Evaluations

All summary of study procedures and evaluations at each visit were provided in Tables 1 and 2 (previous chapter).

6.2.1 Screening, Enrolment and Baseline

An informed consent form must be signed prior to initiating any procedures or evaluations for the purpose of the study (**Appendix B**). After the informed consent form has been signed patients will be randomized to receive FMT for the first 6 months of the study or to be a standard per treatment control group that will received treatment at the last 6 months of the study.

The following evaluations at baseline visit and prior to FMT will be performed in both groups:

- Medical history;
- Vital signs (including pulse, respiration rate, blood pressure and temperature);
- Physical Exam (including weight in kg);
- Concomitant medications;
- Dietary history;

- Expanded Disability Status Score (EDSS);
- Blood samples will be taken for haematology (including haemoglobin, red blood cell count, white blood cell count, differential and platelets);
- Blood samples will be taken for serum chemistry (sodium, potassium, chloride, uric acid, creatinine, blood urea nitrogen, total protein, calcium, albumin, total bilirubin, AST, ALT, alkaline phosphatase, glucose);
- Blood sample for multiplex cytokine profiling (includes pro-inflammatory (IL-6, IL-15, IL-17, GM-CSF, TNF α) and anti-inflammatory (IL-4, IL-10 and IL-14) cytokines).
- Clean catch, mid-stream urine for urinalysis and micro analysis (including pH, protein, glucose, ketones, nitrites, leukocyte esterase, RBCs, WBCs) and gut permeability;
- Blood sample for blood bacterial DNA
- Head MRI as baseline

After evaluation, the FMT via rectal enema will be performed by a RN in each visit.

